3.1 Characteristics

This is a single center pilot study in patients with thyroid cancer. Eligible participants will receive a one-time administration of ^{68}Ga -PSMA-11 and undergo a whole-body PET/MRI imaging study. Patients may undergo an additional follow-up ^{68}Ga -PSMA-11 PET/MRI 2-6 months after the initial imaging study, if they give consent.

3.2 Number of Subjects

The total sample size is 40 patients enrolled over approximately 24 months.

3.3 Eligibility Criteria

Patients must have baseline evaluations performed prior to the first dose of study drug and must meet all inclusion and exclusion criteria. In addition, the patient must be thoroughly informed about all aspects of the study, including the study visit schedule and required evaluations and all regulatory requirements for informed consent. The written informed consent must be obtained from the patient prior to enrollment. The following criteria apply to all patients enrolled onto the study unless otherwise specified.

3.3.1 Inclusion Criteria

1. History of thyroid cancer
2. Whole body ^{18}F -FDG PET/CT, I-123 or I-131 scintigraphy within the past 360 days of the scheduled ^{68}Ga -PSMA PET demonstrating uptake.
3. Age 18 years or older at the time of study entry
4. Creatinine $\leq 3.0 \text{ mg/dL}$
5. Ability to understand a written informed consent document, and the willingness to sign it

3.3.2 Exclusion Criteria

1. Patients who have had active infection within 15 days of study enrollment that may be considered to interfere with ^{68}Ga -PSMA PET imaging by the study investigators.
2. Patients who are unable to have placement of intravenous line access.
3. Pregnant or breastfeeding women.
4. Patients not capable of undergoing a PET/MRI study due to weight, claustrophobia, or inability to lie still for the duration of the exam.

3.4 Study Timeline

3.4.1 Primary Completion

The study is expected to reach primary completion 24 months from the time the study opens to accrual.

3.4.2 Study Completion

The study is expected to reach completion 24 months from the time the study opens to accrual.

4 Imaging Agent

⁶⁸Ga-PSMA is a radiopharmaceutical that will be produced in the Department of Radiology and Biomedical Imaging Radiopharmaceutical Facility. The radiopharmaceutical will be prepared in the same facility in which the administration will take place, the UCSF China Basin Imaging Center, using a germanium-68 generator.

5 Study Procedures and Observations

5.1 Dosage and Administration

⁶⁸Ga-PSMA will be administered on an outpatient basis. It will be administered at a single time point, intravenously, prior to PET imaging. The one-time nominal injected dose will be approved by the UCSF Radiation Safety Committee (RSC) and will be 3 to 7 mCi.. A simultaneous whole body PET/MRI will be used for attenuation correction and anatomic localization of ⁶⁸Ga-PSMA uptake and SUV calculation. ⁶⁸Ga-PSMA is currently in use at UCSF under an IND in prostate cancer with over 300 patients injected and no significant adverse events. Additionally, this radiotracer has been used safely in Europe with over a thousand studies performed without a significant adverse event. For this protocol, ⁶⁸Ga-PSMA will cross reference the currently active IND for prostate cancer that is being used at UCSF. A neck MRI with gadolinium (MR) will be performed at the time of the PET imaging. Gadolinium contrast will not be administered if the patient cannot receive contrast based on Radiology Department guidelines.

5.1.1 Screening Assessments

The Screening procedures and assessments must be completed within 28 days of the Day 1 Visit, unless otherwise noted.

A written, signed, informed consent form (ICF) and a Health Insurance Portability and Accountability Act (HIPAA) authorization must be obtained before any study-specific assessments are initiated. A copy of the signed ICF will be given to the subject and a copy will be filed in the medical record. The original will be kept on file with the study records.

All patients who are consented will be registered in OnCore®, the UCSF Helen Diller Family Comprehensive Cancer Center Clinical Trial Management System (CTMS). The system is password protected and meets HIPAA requirements.

In addition to OnCore, REDCap will be used to collect data for this study. REDCap is a secure, HIPAA-compliant, web-based system.

- Complete medical history
- Baseline standard staging diagnostic exams may be done approximately 360 days before PSMA PET as clinically indicated. Patients may receive staging scans and ⁶⁸Ga-PSMA PET imaging on the same day if the patient meets eligibility criteria for the study as assessed by the Principal Investigator prior to the completion of the scan.
- Pregnancy testing in women of childbearing potential (WOCBP)
- Creatinine
- Thyroglobulin

5.1.2 Study Period

5.1.2.1 ^{68}Ga -PSMA PET/MRI

Subjects will be injected with ^{68}Ga -PSMA [REDACTED] and, if needed, transported to the imaging site. After the biodistribution period (50 to 80 minutes after radiotracer injection), coverage for the scan will extend from the patient's vertex through the thighs.

A standard neck MRI will be performed concurrently with the PET/MRI. This MRI will be performed without and with gadolinium contrast intravenously. Gadolinium contrast will not be administered if the patient cannot receive contrast based on Radiology Department guidelines. A whole body (vertex to toes) MRI (PET/MRI) will be performed for attenuation correction and anatomic localization. Patients may be given lorazepam as needed, to keep them from feeling anxious during the scan. The entire imaging study will take roughly 60 minutes. Imaging will be performed at [REDACTED] UCSF [REDACTED].

No formal report of the findings from imaging studies will be created. Each study will be reviewed by a board-certified nuclear medicine physician and a board-certified radiologist within two working days of the completion of the study. ^{68}Ga -PSMA PET results will not be used for clinical care. If any unexpected findings are visualized, these will be reported to the treating health care provider, who will then contact the patient if additional work-up needs to be performed.

5.1.3 Pathology

In those patients with adequate archival Formalin-Fixed Paraffin-Embedded (FFPE) tissue, analysis will be performed retrospectively when available after successful completion of ^{68}Ga -PSMA PET.

5.1.4 Optional repeat scan

An optional follow up ^{68}Ga -PSMA PET study may be obtained between 2 and 6 months after completion of the first PET. Optional PET will be performed to determine any interval changes in PSMA uptake and compare them to clinical changes including thyroglobulin. The potential for follow-up examination will be discussed and consented for during the original consent process. The study team will contact the patient after completion of the PET about repeat imaging. Sections 5.1.2 and 5.1.3 will be followed during the follow-up imaging.

A maximum number of two ^{68}Ga -PSMA studies (initial and optional follow up) will be performed under this protocol.

Period/ Procedure	Screening	Imaging	Optional Imaging
Study Day/Visit Day	-28 to 1	D1	2-6 months after 1st ⁶⁸Ga- PSMA PET
Informed consent	X		
AE assessment			X ²
Concomitant medications	X	X	X ²
Clinical procedures			
Medical history including prior/concomitant systemic therapies for thyroid cancer	X		
Laboratory procedures			
Creatinine	X		
Thyroglobulin	X		
Pregnancy test (HCG) (WOCBP only)	X		
Imaging procedures			
Standard diagnostic scans as clinically indicated ¹	X ¹		
⁶⁸ Ga-PSMA-11 administration		X	X ²
Whole body PET/MRI		X	X ²

1. Standard of care PET scan may be done up to 360 days before PSMA PET. Patients may receive staging scans and 68Ga-PSMA PET imaging on the same day if the patient meets eligibility criteria for the study as assessed by the Principal Investigator prior to the completion of the scan.
2. Only required if patient agrees to optional follow-up 68Ga-PSMA PET.

6 Reporting and Documentation of Results

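### No pregnancy test is scheduled before the optional second 68Ga-PSMA-11 injection, when the last scheduled test could be about 61 to 211 days old

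*Combined protocol and SAP*

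**What the plan says.** Section 3.3.2 lists "Pregnant or breastfeeding women" among the exclusions. Section 5.1.1 places the pregnancy test among the screening assessments, with this timing: "The Screening procedures and assessments must be completed within 28 days of the Day 1 Visit, unless otherwise noted".

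Section 3.3 contains two statements that matter here. One concerns timing: "Patients must have baseline evaluations performed prior to the first dose of study drug". The other concerns scope: "The following criteria apply to all patients enrolled onto the study unless otherwise specified".

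For the optional repeat scan, 5.1.4 states: "Sections 5.1.2 and 5.1.3 will be followed during the follow-up imaging". Section 5.1.2 covers the PET/MRI and 5.1.3 covers archival tissue. Consent for the repeat scan is taken as part of the original consent.

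In the schedule table, the row "Pregnancy test (HCG) (WOCBP only)" has a single mark, in the Screening column. The Optional Imaging column is marked for adverse event assessment, concomitant medications, tracer administration and whole body PET/MRI.

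**The concern.** The protocol treats pregnancy as a reason not to inject and uses an HCG test to enforce that. It then allows a second injection of the same tracer, months later, without scheduling the test again. Read as written, the exclusion still holds for a woman known to be pregnant, but nothing in the schedule would reveal a pregnancy that neither she nor the study team knew about.

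What is at stake is participant safety: possible exposure of an unrecognised pregnancy to the radiotracer. The second scan is optional and section 5.1.2 says the PSMA PET results will not guide clinical care, so clinical need does not justify a weaker safeguard at that visit. This is an omission in the schedule and does not contradict any other part of the plan.

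**Working it through.** **Is a test scheduled anywhere before the second injection?**

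| Place | What it provides at the repeat visit |
|---|---|
| 3.3 | Baseline evaluations are tied to the first dose; the criteria cover all enrolled patients, with no step to verify them again |
| 5.1.1 | Contains the pregnancy test, but 5.1.4 does not name this section for the repeat scan |
| 5.1.2 | Applied at the repeat scan; no pregnancy test or eligibility check |
| 5.1.3 | Applied at the repeat scan; tissue analysis only |
| Schedule table, Optional Imaging | Tracer administration marked; HCG not marked; medical history not marked |

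The single HCG mark is unlikely to be a displaced Optional Imaging entry. Every entry in that column carries footnote 2, and the HCG mark has no footnote. The text of 5.1.1 and 5.1.4 gives the same answer without the table.

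**How old would the last scheduled test be?**

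The plan states no figure for this, so there is none to reproduce. Inputs:

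- Time from test to Day 1: 0 to 28 days (5.1.1; the table gives -28 to 1).
- Time from first to second scan: 2 to 6 months (5.1.4).
- Month length (assumption): 365.25 / 12 = 30.4375 days.

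Age of test = (days from test to Day 1) + (days from first to second scan).

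- Shortest: 0 + 2 × 30.4375 = 60.9, about 61 days.
- Longest: 28 + 6 × 30.4375 = 28 + 182.6 = 210.6, about 211 days.

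Relative to the 28-day window for the first dose: 60.875 / 28 = 2.2 and 210.625 / 28 = 7.5.

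**Sensitivity to the day count**

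- Calendar months: 2 months is 59 to 62 days and 6 months is 181 to 184 days, so the range is 59 to 184 + 28 = 212 days.
- 30-day months: 60 to 180 + 28 = 208 days.
- Counting 29 days from Day -28 to Day 1: the upper end becomes 182.6 + 29 = 211.6, about 212 days, or 184 + 29 = 213 with calendar months.

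Under each of these conventions, even the shortest interval is more than twice 28 days.

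**The case against.** The best case against the point has five parts.

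1. **The table may not be a complete list of what is done at the repeat visit.** Section 5.1.4 plans to compare changes in uptake with clinical changes including thyroglobulin, yet thyroglobulin is also marked only at Screening. Adverse event assessment is marked only at the optional visit. This limits the claim to what is scheduled and says nothing about what staff would do in practice. It also suggests that the laboratory rows were simply not carried over, which is the omission described here.

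2. **A safeguard may sit outside the visible text.** It could be in the consent form, the cross-referenced IND, the Radiation Safety Committee's conditions or local radiology practice. None of these can be seen. The one departmental rule that is visible covers contrast only: "Gadolinium contrast will not be administered if the patient cannot receive contrast based on Radiology Department guidelines". It does not cover the tracer. If local practice already requires a test, writing it into the protocol costs almost nothing.

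3. **The exclusion applies to every enrolled patient and is not limited to the first dose.** That is right, and it covers a known pregnancy. It does not supply a means of finding an unknown one.

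4. **The interval does not measure risk.** This stands. The figure of 61 to 211 days is the visit window plus the screening window. It does not say how many women are affected or how likely a new pregnancy is, and the Abstract calls the timing approximate, so neither end is a hard limit.

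5. **Repeating the 28-day window would still miss a pregnancy that began after the test.** This also stands. The same limit applies to the first dose.

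**Conclusion.** The point holds. The visible protocol schedules no pregnancy test before the second injection, and the last scheduled one would be about 61 to 211 days old (59 to 213 days across the conventions tried), or about 2.2 to 7.5 times the 28-day window set for the first dose. These figures rest on an assumed month length and on the 2 to 6 month window being kept.

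The gap applies only to women of childbearing potential who accept the optional scan, and their number is not given. It bears on participant safety alone.

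The creatinine criterion (at most 3.0 mg/dL) is likewise not rechecked. That is a minor matter: contrast at the repeat scan is already under the departmental rule, and the documents state no renal hazard for the tracer.

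**What to change.** By amendment:

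1. In the schedule table, mark the HCG row under Optional Imaging for women of childbearing potential, to be done within 28 days before the second injection. This matches the standard for the first dose. A test on or near the injection day would leave a shorter gap, if the team is willing to go beyond that standard.
2. Add one sentence to 5.1.4 requiring that the pregnancy and breastfeeding exclusion in 3.3.2 be reconfirmed before the second injection.
3. Optionally, mark creatinine in the same column, and leave contrast to the existing departmental rule.

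The cost is one table cell, one sentence and one extra HCG test for each woman of childbearing potential who takes the optional scan. If item 3 is adopted, add one creatinine test for each participant who takes it. A woman who tests positive would lose the optional scan, as the exclusion intends.

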6.1 Definitions

Evaluable for toxicity

All patients will be evaluable for toxicity from the time of ⁶⁸Ga-PSMA administration.

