6.2 Evaluation of Safety

Analyses will be performed for all patients having received ⁶⁸Ga-PSMA. The study will use the [CTCAE v4.0](#) for reporting of adverse events.

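### The study calendar schedules adverse-event assessment only at the optional repeat scan, not at the first administration that every patient receives

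*Combined protocol and SAP*

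**What the plan says.** The calendar at the end of section 5.1.4 has three columns: Screening, Imaging (D1) and Optional Imaging, the last falling 2 to 6 months after the first scan. In the row "AE assessment" the Screening and D1 cells are empty. The only mark is under Optional Imaging and carries footnote 2: "Only required if patient agrees to optional follow-up 68Ga-PSMA PET".

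The same calendar marks administration of the agent at D1 without condition, and section 3.1 has every eligible participant dosed at the initial scan.

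On the repeat scan, section 5.1.4 says "Sections 5.1.2 and 5.1.3 will be followed during the follow-up imaging".

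On safety, section 6.1 begins "All patients will be evaluable for toxicity from the time of" and goes on to name administration of the agent. Section 6.2 begins "Analyses will be performed for all patients having received" and again refers to the agent. Neither section makes the repeat scan a condition.

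**The concern.** The calendar tells site staff what to do at each visit. Followed literally, it asks for no adverse-event assessment at the one administration that all patients receive, and asks for one only from patients who volunteer for a second. A patient who declines the repeat scan has no scheduled assessment at all. A patient who accepts has a single one, 2 to 6 months after the first dose.

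That does not fit a safety population made up of everyone dosed and evaluable from the moment of dosing. For one-scan patients the safety data would rest on events that happen to be noticed or volunteered, and an absence of recorded events could not be read as an absence of events. Section 8.3 also requires the investigator to alert the data and safety monitoring committee if Grade 3 or 4 events become more frequent than the Investigator Brochure or package insert reports. That comparison depends on how completely events are found in dosed patients.

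**Working it through.** The plan gives no figure to reproduce. The check is a comparison of the calendar with the text, followed by a simple count.

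**1. The calendar, row by row.** Four rows carry a footnote 2 mark at the optional scan:

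| Row | Screening | Imaging D1 | Optional Imaging |
|---|---|---|---|
| Adverse-event assessment | blank | blank | X, footnote 2 |
| Concomitant medications | X | X | X, footnote 2 |
| Administration of the agent | blank | X | X, footnote 2 |
| Whole-body PET/MRI | blank | X | X, footnote 2 |

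Three of the four are also marked at D1. Adverse-event assessment is the exception. The two imaging rows keep their D1 mark after a blank Screening cell, so the D1 column as a whole survived the reading of the PDF. The adverse-event mark has not simply slipped over from D1, because its footnote makes sense only in the optional column.

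**2. Is there a reason for the difference?** Section 5.1.4 applies the same imaging procedures at the repeat scan as at the first. Section 5.1.2, which describes those procedures, contains no adverse-event check. No section explains why events would be assessed at the second administration but not the first.

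**3. Does another section schedule the missing enquiry?**

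- Sections 6.4 and 8.3 require events to be recorded (grade 3 and above in 6.4, clinically significant in 8.3). Neither names a visit or a time window for finding them.
- Section 6.5 requires events to be followed until resolved, which presupposes that they are known.
- Section 6.6 gives a 30-day window, for expedited reporting of related deaths only.
- Section 5.1.4 does provide for a contact after the first scan, but its stated purpose is the repeat scan: "The study team will contact the patient after completion of the PET about repeat imaging".
- The abstract gives duration of follow-up as not applicable.

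None of these fills the gap.

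**4. Count.** Inputs: 40 patients (section 3.2), all dosed at D1 (section 3.1 and the calendar), and a cap on scans per patient (section 5.1.4, "A maximum number of two"). Expected uptake of the repeat scan is not stated, so let k patients repeat, with k assumed anywhere from 0 to 40. Total administrations are then 40 + k.

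- First administrations with a scheduled assessment at that visit: 0 of 40.
- Share of all administrations with a scheduled assessment at the same visit: k/(40 + k).
- Share of patients with any scheduled assessment: k/40.

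| k | k/(40 + k) | k/40 |
|---|---|---|
| 0 | 0/40 = 0% | 0% |
| 10 | 10/50 = 20% | 25% |
| 20 | 20/60 = 33% | 50% |
| 40 | 40/80 = 50% | 100% |

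With D1 also marked, the shares become (40 + k)/(40 + k) = 100% and 40/40 = 100% for every k.

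**The case against.** The strongest reply is that the point rests on one blank cell in a table read from PDF. That the other three rows are marked at D1 could itself suggest a mark dropped in the source or in the reading, not a decision to leave the assessment out. This possibility cannot be closed from the text and lowers confidence to medium. If the mark was dropped in the source, the remedy is the same. If it was lost only in the reading, the sponsor can settle the matter by looking at the page.

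Second, sections 6.1 and 6.2 say who is evaluable and who is analysed, not how or when events are found, so the calendar might be called incomplete, not contradictory. The calendar does more than stay silent, however. Through footnote 2 it sets a condition on adverse-event assessment that would exclude patients whom 6.1 and 6.2 include.

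Third, sections 6.4, 6.5 and 8.3 oblige the team to record, follow and review events in every dosed patient, and the patient is on site at D1 for the uptake period and the scan. This stands, and it means that safety oversight is not absent. What is missing is a scheduled enquiry.

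Fourth, the stakes are modest. Section 8.3 rates the risk as low, section 5.1 reports over 300 earlier injections at the site without a significant adverse event, and neither the objectives nor section 6.10 calls for an adverse-event rate. All of this stands and limits the weight of the point. It does not explain assessing only the optional dose.

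Finally, the shares above follow mechanically from the blank cell and do not measure missed events. That is correct, and they should be read only as coverage of the schedule. The assessment at the repeat visit might be meant to look back over the interval since the first dose. Even so, it would miss every patient who declines.

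**Conclusion.** The concern holds, with medium confidence. As written, the calendar ties adverse-event assessment to acceptance of the repeat scan and so does not fit the safety population of sections 6.1 and 6.2. None of the 40 planned first administrations has a scheduled assessment. Coverage of administrations at the same visit cannot exceed 50%, and it falls to 0% if nobody repeats.

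Two assumptions carry this: that the D1 cell is blank in the source table, and that k can lie anywhere from 0 to 40. The consequence is confined to safety ascertainment. No bias in a planned estimate is claimed. The correction should be made, but the point does not threaten the study's objectives.

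**What to change.** Check the D1 cell in the source table. If it is blank there, reconcile the calendar with sections 6.1 and 6.2 by marking adverse-event assessment at Imaging D1 for all patients, and keep the existing mark at the optional scan. Because 6.1 starts evaluability at administration, the D1 assessment has to come after the injection. Stating the period that each assessment covers would be a useful but optional clarification.

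The cost is one calendar mark. The D1 visit already takes place and the row "Concomitant medications" is already marked there, so no visit is added. Under section 7.4 the change needs an amendment approved by the Protocol Review Committee and the IRB, and it could travel with any other amendment.

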6.1 Definitions

Evaluable for toxicity

All patients will be evaluable for toxicity from the time of ⁶⁸Ga-PSMA administration.

